#### 6.3. Safety Set

All patients who received at least one dose of study drug will be included in the Safety Set. Patients will be considered, for safety analysis, to be in the treatment cohort of the treatment they actually received.

#### 6.4. PK Analysis Set

The PK Analysis Set will be described in a separate PK analysis plan.

## 7. STATISTICAL ANALYSIS

For the statistical analyses below, descriptive statistics (n, mean, median, standard deviation [SD], 95% confidence interval [CI], minimum, and maximum) will be provided for each continuous variable, and frequencies and percentages will be provided for each categorical variable. Analyses will be conducted using Statistical Analysis Software (SAS©) version 9.2 or higher. Any hypothesis testing described will be 2-sided and performed at the 0.05 level of significance; p-values <0.05 will be considered statistically significant. In general, analyses will be presented by treatment cohort, and overall where specified. The 3 treatment cohorts are listed below:

Cohort #	Description	Label in output
Cohort 1:	Asfotase alfa 0.5 mg/kg initial single dose; followed by multiple dosing starting after 2 weeks at 0.5 mg/kg 3 times per week	0.5 mg/kg cohort
Cohort 2:	Asfotase alfa 2.0 mg/kg initial single dose; followed by multiple dosing starting after 2 weeks at 2.0 mg/kg 3 times per week	2.0 mg/kg cohort
Cohort 3:	Asfotase alfa 3.0 mg/kg initial single dose; followed by multiple dosing starting after 2 weeks at 3.0 mg/kg 3 times per week	3.0 mg/kg cohort

#### 7.1. Study Patients

#### 7.1.1. Disposition of Patients

The number and percent of patients completing the study will be described. For patients who discontinued the study, the reason for discontinuation will be summarized. In addition, the number of patients who discontinued study drug permanently due to an AE will be summarized. Information will be reported using all randomized patients and summary statistics will be presented by treatment cohort and overall.

A listing of patients indicating randomization to treatment, attendance at each visit (home or inclinic), discontinuation from the study, and completion of the study will also be generated.

#### 7.1.2. Protocol Deviations

The number and percent of patients with specific protocol deviations will be summarized using all randomized patients. The following protocol deviations will be checked programmatically from the database:

- 1. Patients who violated any inclusion/exclusion criteria.
- 2. Patients who missed one of the scheduled doses of study drug.
- 3. Patients who did not receive the correct study treatment.

4. Patients who received doses outside the 10% window for expected mg dosage administration.

Protocol deviations from monitoring reports and other relevant sources will also be reviewed, and any important deviations will be included in the list that is summarized and reported.

Summary statistics will be presented by treatment cohort and overall.

#### 7.1.3. Demographics, Disease Characteristics, and History

All demographic, baseline characteristic, and history information will be summarized using the FA Set by treatment cohort and overall. No formal hypothesis testing will be performed to compare differences between treatment cohorts.

Summary statistics will be presented using descriptive statistics (n, mean, SD, 95% CI, median, minimum, and maximum) or frequencies and percentages, as appropriate.

#### 7.1.3.1. Demographics

The following demographic variables will be summarized:

- Sex
- Ethnicity
- Race
- Japanese descent (yes/no)
- Age (years) at Enrollment
- Age (years) at First Injection

#### 7.1.3.2. Disease Characteristics

The following disease characteristics will be summarized:

- Age at First Sign/Symptom (years)
- Age at Diagnosis (years)
- Time since First Sign/Symptom (see Appendix 9.3)
- Time since Diagnosis (see Appendix 9.3)
- TNSALP Gene Mutation
  - Method of Sequencing (whole exome/gene/targeted mutation/targeted next generation/panel/other/unknown)
  - Polymorphism present (yes/no)
  - Polymorphism status (homozygous/heterozygous)
- Documented history (yes/no) of:
  - serum alkaline phosphatase (ALP) levels below the age-adjusted normal range
  - tissue-nonspecific alkaline phosphatase (TNSALP) gene mutation(s)

- documented history of PLP above the upper limit of normal at Screening

All disease characteristics, including the TNSALP gene mutation reported, will be presented by treatment cohort and patient identification in data listings.

#### 7.1.3.3. Medical History and Baseline Physical Examination

The number and percentage of patients with medical history findings will be summarized for the FA Set by treatment cohort and overall by The Medical Dictionary for Regulatory Activities (MedDRA) System Organ Class (SOC) and Preferred Term (PT). Additionally, HPP-specific medical history will be summarized, including a summary of first known HPP symptoms. Lastly, the number of permanent teeth lost and number of episodes of pneumonia will be summarized.

For the physical examination, the number and percentage of patients with abnormal findings at Baseline for each body system will be summarized by treatment cohort and overall.

All medical history and baseline physical examination data will be presented in by-patient data listings, including the medical history verbatim text describing each history event or first known symptom and any abnormal physical examination free text findings. Height at study entry and postmenopausal status for females at study entry will also be presented in listings.

#### 7.1.4. Prior and Concomitant Medications / Therapies

Concomitant medication/therapy data and prior- medication data will be presented in by-patient data listings. See Appendix 9.1 for additional details on the definition of prior and concomitant medications/therapies and rules for handling missing or incomplete start and stop dates. Concomitant medications and therapies will also be summarized in tabular form by anatomic class (ATC) level 3 and generic name for the FA Set by treatment cohort and overall using frequencies and percentages. The WHO Drug dictionary (DD) version from MAR2015 or later will be used to code the medications.

# 7.2. Efficacy/Pharmacodynamic Analyses

The analyses and summaries will be based on the FA Set.

#### 7.2.1. Primary Endpoint

The primary endpoint for this study is the change in PPi from Baseline to pre-3rd dose Week 9. Change from Baseline in PPi will be the primary variable. Primary analysis will be performed by using a restricted maximum likelihood (REML)-based repeated measures mixed model, fit for each treatment cohort to estimate the change at each pre-dose (trough) timepoint starting at Week 4 (Day 22) through Week 9 (Day 61). The primary hypotheses will test whether the differences between the cohorts differ from zero at pre-3rd dose Week 9. The Week 3 (Day 15) pre-dose timepoint will not be included in the model assessing change since this is expected to be similar to a baseline level of PPi after the first non-dosing period. The analysis will include the fixed, categorical effect of visit, adjusted for baseline PPi, gender, baseline weight group ( $\geq$  median versus < median), and study drug lot assignment. An unstructured covariance structure will be used to model the within-patient errors. If this analysis fails to converge, the following structures will be tested and the final covariance structure will be determined by Akaike's information criterion (AIC): first-order autoregressive, compound symmetry, and Toeplitz. The Kenward-

Roger approximation will be used to estimate denominator degrees of freedom. The estimated mean change from Baseline at each visit from the model will be provided, along with 95% CIs and p-values.

A fixed sequence testing procedure will be performed with the comparison of the 3.0 mg/kg cohort compared with the 0.5 mg/kg cohort being performed first, and the hypothesis testing for the second comparison 2.0 mg/kg cohort compared with the 0.5 mg/kg cohort only being performed if the null hypothesis is rejected for the previous comparison at a significance level of 0.05 (p-value <0.05). The primary endpoint will be met if the null hypothesis is rejected for both comparisons at a significance level of 0.05 (both p-values <0.05).

The same model will additionally be employed with the fixed, categorical effect of visit, adjusted for baseline PPi.

A similar modeling approach will be employed to explore the effect of treatment cohort on the change from Baseline in PPi at each pre-dose timepoint.

As supportive analysis, the non-parametric exact Wilcoxon rank-sum test will be used to assess differences between treatment cohorts, using both last observation carried forward (LOCF) and observed case (OC) methods. The location shift in the change from Baseline distributions and 95% CI for the above comparisons will be reported using the Hodges-Lehmann-Sen estimate and the exact confidence limits reported.

To examine the change from Baseline in PPi, descriptive statistics for the absolute PPi level and the change from Baseline will be summarized at all study timepoints by treatment cohort, spanning from Week 1 to Week 13; Baseline will be calculated in the same way as for the primary analysis. Within cohort, the change from Baseline to all study timepoints will be analyzed using the non-parametric Wilcoxon signed-rank test.

Individual and mean PPi levels for each cohort versus time curves will be presented with normal references ranges indicated (see Appendix 9.3). Please refer to Table 4 on how to handle the values fall under the lower limit of quantification (LLOQ). Additional analysis of PPi data may be performed if considered useful.

The above analyses for PPi will additionally be performed using the PP Set.

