## 11.5.4. Efficacy/Pharmacodynamic Analyses

## 11.5.4.1. Primary Efficacy/Pharmacodynamic Endpoint

The primary efficacy/PD endpoint will be the change from PPi Baseline to pre-3rd dose Week 9. Baseline is defined as the average of all available Run-in Period assessments on or prior to first SC injection with asfotase alfa. Pre-3rd dose Week 9 is defined as the value obtained prior to the third dose during Week 9. To assess differences between cohorts, the Wilcoxon rank-sum test will be used. A fixed sequence testing procedure will be performed with the comparison of the 9.0 mg/kg/week cohort compared to the 1.5 mg/kg/week cohort being performed first, and the hypothesis testing for the second comparison 6.0 mg/kg/week cohort compared to the 1.5 mg/kg/week cohort only being performed if the null hypothesis is rejected for the previous comparison at a significance level of 0.05. The primary endpoint will be met if the null hypothesis is rejected for both comparisons at a significance level of 0.05. Additionally, the shift in the distributions and 95% confidence interval (CI) for the above comparisons will be reported using the Hodges-Lehmann-Sen estimate and the exact confidence limits reported.

As secondary analyses, descriptive statistics for absolute PPi level and the change from Baseline will be summarized at all study timepoints by cohort. Within cohort, the change from Baseline to all study timepoints will be analyzed using the Wilcoxon signed-rank test.

Additionally, a restricted maximum likelihood (REML)-based repeated measures mixed model will be fit to estimate the change from Baseline in PPi at each pre-dose timepoint during the study period and test whether the change differs from zero at each timepoint. The analysis will include the fixed, categorical effect of visit. An unstructured covariance structure will be used to model the within-patient errors. If this analysis fails to converge, the following structures will be tested and the final covariance structure will be determined by Akaike's information criterion (AIC): first-order autoregressive, compound symmetry, and Toeplitz. The Kenward-Roger approximation will be used to estimate denominator degrees of freedom. The estimate of change from Baseline at defined visits will be provided, along with 95% CIs and p-values. The treatment effect will also be explored.

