# 4.1. Changes from Analyses Specified in the Protocol

The primary analysis of the primary endpoint, the change in PPi from Baseline to pre-3rd dose Week 9 has been changed from non-parametric exact Wilcoxon rank-sum test into a restricted maximum likelihood (REML)-based repeated measures mixed model; while non-parametric exact Wilcoxon rank-sum test becomes a supportive analysis.

The Per Protocol Set criteria for study drug compliance has been modified as 100% compliance (i.e. all doses of study drug) is too restrictive. A slightly revised definition will be utilized requiring that patients receive 100% of study drug as planned on Weeks 8 and 9, and at least 80% of study drug overall as specified in the protocol.

All prior and concomitant medications and therapies must be collected from 30 days prior to study entry up until the final study visit. The protocol has inconsistent description of the process for the collection of Concomitant medications and therapies in Table 2, footnote 9 and Section 8.7; this is being clarified with an administrative letter.

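### The SAP's primary mixed model is described as fitted for each cohort with no cohort term, so the model term behind the two deciding between-cohort tests is not stated

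*SAP*

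**What the plan says.** SAP 7.2.1 describes the primary analysis as a REML "repeated measures mixed model, fit for each treatment cohort to estimate the change at each pre-dose (trough) timepoint", covering Week 4 (Day 22) through Week 9 (Day 61). The target is comparative: "The primary hypotheses will test whether the differences between the cohorts differ from zero at pre-3rd dose Week 9". The order is 3.0 vs 0.5 mg/kg, then 2.0 vs 0.5 mg/kg, and both must reach two-sided p<0.05.

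The terms are given as follows: "The analysis will include the fixed, categorical effect of visit, adjusted for baseline PPi, gender, baseline weight group", followed by study drug lot. Covariance is unstructured, with a fallback: "If this analysis fails to converge, the following structures will be tested", namely first-order autoregressive, compound symmetry and Toeplitz, chosen by AIC. Degrees of freedom are Kenward-Roger. The output named for the model is the mean change from Baseline at each visit, with confidence intervals and p-values.

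Two further sentences matter. A reduced version is planned: "The same model will additionally be employed with the fixed, categorical effect of visit, adjusted for baseline PPi". Then: "A similar modeling approach will be employed to explore the effect of treatment cohort on the change from Baseline in PPi at each pre-dose timepoint".

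In Protocol 11.5.4.1 the two-sample Wilcoxon test was primary. The mixed model there was an additional analysis meant to "test whether the change differs from zero at each timepoint. The analysis will include the fixed, categorical effect of visit". SAP 4.1 promotes the mixed model, "while non-parametric exact Wilcoxon rank-sum test becomes a supportive analysis".

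**The concern.** Both p-values that decide the primary endpoint are differences between cohorts. A model fitted inside one cohort estimates that cohort's mean changes; it has no parameter for a difference from another cohort. If three models are fitted, something must say how two of them are combined: at which covariate values, with what standard error and with what degrees of freedom. If one model is fitted to everybody, a cohort term must be in it, and a cohort-by-visit term is needed for the difference to be specific to Week 9. The SAP states neither.

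The wording looks like a remnant of the protocol's test of change against zero, which became primary when the two-sample test was demoted. The trial is open-label (Protocol 8.6), so leaving this choice to programming leaves discretion over the deciding tests. PLP inherits the gap, because SAP 7.2.2 relies on similar methods.

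**Working it through.** **1. The plan's own figure.** SAP 9.2 bases power on a two-sample t-test, which does contain a between-cohort difference. Noncentrality = δ / (SD·√(2/n)), df = 2n-2.
- n=9, δ=2.3, SD=1.5: 2.3 / (1.5·√(2/9)) = 2.3/0.707 = 3.25, df 16, power 86% (plan: >80%).
- n=6, δ=3.2: 3.2 / (1.5·√(2/6)) = 3.2/0.866 = 3.70, df 10, power 91% (plan: >90%).

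Both stated figures are reproduced, per comparison.

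**2. Readings that the text leaves open.**
- (a) Separate fits, combined by an unstated rule.
- (b) A joint model with a cohort main effect only. Its contrast is averaged over visits and is not specific to Week 9.
- (c) A joint model with cohort, visit and cohort-by-visit. Only this one yields the stated hypothesis directly.

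**3. Between-patient residual df.** Covariate columns p = baseline PPi (1) + gender (1) + weight group (1) + lots minus 1. The number of lots is not given; two are assumed, so p = 4.
- Separate fit: n-1-p = 9-1-4 = 4 per cohort.
- Joint fit: 27-3-4 = 20.
- With three lots: 3 against 19.
- With the minimum of 6 per cohort and two lots: 6-1-4 = 1 against 18-3-4 = 11.

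**4. Unstructured covariance in a 9-patient fit.** Scheduled pre-dose visits from Day 22 through Day 61 are Days 22, 29, 43, 50, 57 and 61. That gives T = 6 and 6·7/2 = 21 covariance parameters (15 if Day 57 is left out). With one slope per covariate across visits and complete data, the T-1 between-visit differences use up df alongside the covariates. Estimation needs n-1-p-(T-1) = n-p-T ≥ 1.
- T=6, p=4: 9-4-6 = -1, not estimable.
- T=6, p=3 (one lot in the cohort): 9-3-6 = 0, not estimable.
- T=5, p=4: 9-4-5 = 0, not estimable.
- T=5, p=3: 9-3-5 = 1, estimable.
- Joint model, T=6, p=4: 27-3-4-5 = 15, estimable.

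The fallback structures may solve convergence, but they do not supply the contrast.

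**5. Does the reading change the test?** This is a simulation of the 3.0 vs 0.5 mg/kg comparison using Day 61 only, with 20,000 trials per setting. From the plan: 9 per cohort, 2.3 μM, SD 1.5 μM. Assumed: complete data; two lots; weight group and lot allocated at random; gender nearly balanced; no effect of gender, weight group or lot; correlation ρ between baseline and change of 0 or -0.5. Change = 1.5·(ρz + √(1-ρ²)·e) + δ, where z is standardised baseline and e is standard normal. Separate fits are combined by adding variances with Satterthwaite df.

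| Reading | Power, ρ=0 | Power, ρ=-0.5 |
|---|---|---|
| Joint model | 82% | 91% |
| Separate fits, common covariate values | 61% | 73% |
| Separate fits, own-cohort covariate means | 79% | 87% |

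With no true difference, own-cohort means reject in about 7% of trials at ρ=-0.5; the joint model stays near 5%. The reason is simple. At its own covariate means a cohort's adjusted mean is just its raw mean, so the difference is unadjusted with true standard error 1.5·√(2/9) = 0.707. The standard error used has the baseline effect removed: about 0.707·√(1-0.25) = 0.612.

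In about 4% of trials at least one of the two separate fits had a constant or collinear covariate. These trials are left out of the separate-fit rows.

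**The case against.** The best answer is that a joint model was plainly meant. The sentence after the per-cohort wording sets a between-cohort target, and the section refers to one final covariance structure, which sits badly with three separate fits. The phrase about fitting for each cohort could mean cohort-specific visit means from one model. The exploratory sentence could refer only to the other visits. This makes a joint model the likelier intention. It does not put the term in the plan: the ANCOVA in SAP 7.2.1.5 names treatment as a fixed factor, while the primary model's list does not.

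Some stronger inferences should be resisted.
- A reader might conclude that the whole estimator is undefined. It is not: REML, the covariance hierarchy, Kenward-Roger df, the covariates, the test order and the alpha are all fixed. The cohort term and the contrast are missing.
- A reader might cite the visit-plus-baseline sentence in SAP 4.2 as a second description of the primary model. That sentence matches the additional reduced model; SAP 4.2 refers to SAP 4.1 for the primary change.
- A reader might combine the large power loss with the inflated error rate. They belong to different implementations. The failure to obtain an estimate (about 4% of trials) likewise concerns common covariate values; at own-cohort means with complete data the cohort mean is always available.

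The sensitivity ANCOVA and the supportive exact Wilcoxon test would expose an odd primary result, which limits the harm. Neither decides the endpoint.

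**Conclusion.** The point stands as a specification fault: as written, the primary model does not contain the quantity that the primary hypotheses test. This follows from the text alone and needs no simulation.

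The size depends on the implementation. If a joint model with cohort-by-visit is programmed, nothing is lost. If the wording is followed literally, each fit has about 4 between-patient df instead of 20 (two lots assumed), and an unstructured covariance over six visits cannot be estimated from 9 patients. First-comparison power then runs from 20 or so points below the joint model (common covariate values) to 3-4 points below it (own-cohort means), with about 7% type I error for the latter at a correlation of -0.5.

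These power and error figures are illustrative. They use Day 61 data only and rest on assumed lots, correlations, covariate balance and complete data; the plan's unstructured covariance and Kenward-Roger df were not simulated. They show that the wording matters, not what this trial would lose. A reader might infer that the sponsor planned three separate analyses; the documents do not establish that.

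**What to change.** Before database lock, amend SAP 7.2.1 to state:
- One REML repeated-measures model is fitted to all Full Analysis patients over the same pre-dose (trough) timepoints, Day 22 through Day 61. Fixed effects are cohort, visit, cohort-by-visit, baseline PPi, gender, baseline weight group and study drug lot.
- The primary tests are the 3.0 vs 0.5 and 2.0 vs 0.5 mg/kg differences in least-squares means at the Day 61 pre-dose visit, in the existing fixed sequence.
- Per-cohort mean changes are least-squares means from the same model. The covariance fallback and Kenward-Roger df stay.
- Whether Day 57 is included. The sampling schedule lists it as pre-dose without the trough label. The label alone cannot settle this, since Day 22 lacks it too and is expressly included.
- The reduced model contains cohort, visit, cohort-by-visit and baseline PPi. The exploratory sentence is limited to cohort differences at the other pre-dose visits.

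In SAP 7.2.2, specify the same joint model for PLP with baseline PLP in place of baseline PPi.

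The cost is SAP wording and programming; no new data are needed. The price is an assumption of common covariate effects and a common within-patient covariance across cohorts, which the SAP should acknowledge.

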## 8.4. Rationale for Selection of Doses in the Study

Based on relevant non-clinical data, as well as current human experience with asfotase alfa in patients with hypophosphatasia to date, a dose of 6 mg/kg/week administered subcutaneously is the recommended dose in pediatric patients; this dose regimen has been approved for treatment of pediatric patients with HPP in the US, EU, and other countries.

The dose regimens planned for this study (ie, 1.5 mg/kg/week, 6.0 mg/kg/week, and 9.0 mg/kg/week) bracket the recommended dose regimen in pediatric HPP patients and span a 6-fold dose range from the lowest to the highest dose, allowing the best opportunity to construct dose-response relationships in adult patients with pediatric-onset HPP.

Weight based (ie, mg/kg) dosing for asfotase alfa allows normalization of dosing across patient populations with different body weights (inter-patient) and within the same patient over time (intra-patient).

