#### 7.2.1.4. Hypothesis Testing and Significance Level

A two-sided Type I error rate of 0.05 will be used to define statistical significance. The primary endpoint will be met if the null hypothesis is rejected for both comparisons described in Section 7.2.1 at a significance level of 0.05, i.e. both p-values <0.05. For the primary endpoint, a fixed sequence testing procedure will be used to control the Type I error rate. Statistical adjustment of p-values will not be performed.

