#### 7.2.1.5. Sensitivity Analyses

The change in PPi from Baseline to pre-3rd dose Week 9 will also be analyzed using analysis of covariance (ANCOVA), with treatment as fixed factor, baseline PPi, gender, baseline weight group ( $\geq$  median versus < median), and study drug lot assignment as covariates, and using both LOCF and OC methods in the FA Set.

The tests will compare 2.0 mg/kg cohort to 0.5 mg/kg cohort, and 3.0 mg/kg cohort to 0.5 mg/kg cohort. Ninety-five percent CIs will be presented together with the estimated p-values.

In addition, sensitivity analyses will be performed if any medications are administered to the patient that might impact the results used in the primary analysis of PPi.

Sensitivity analyses may be employed that include only the patients that receive 100% of the study drug doses through Week 9, as specified in the protocol.

Finally, sensitivity analyses may be employed to exclude biologically implausible outliers in PPi and PLP.

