#### 9.2. Sample Size, Power, and Randomization

A sample size of 9 patients per cohort (27 patients total) will provide sufficient power (>80%) to detect a difference of 2.3 µM between the 9.0 mg/kg/week cohort compared to the 1.5 mg/kg/week cohort, and between the 6.0 mg/kg/week cohort compared to the 1.5 mg/kg/week cohort in the change from Baseline to pre-3PrdP dose in Week 9 PPi (assuming a SD of 1.5 μM). This is based upon the use of a 2-sided, 2-sample t-test analyzed using a fixed sequence testing procedure with the comparison of the 9.0 mg/kg/week cohort compared to the 1.5 mg/kg/week cohort being performed first, and the hypothesis testing for the second comparison 6.0 mg/kg/week cohort compared to the 1.5 mg/kg/week cohort only being performed if the null hypothesis is rejected for the previous comparison at a significance level of 0.05.

A sample size of 6 patients per cohort (18 patients total) will provide sufficient power (>90%) to detect a difference of 3.2 µM (SD 1.5 µM) using the same assumptions and fixed sequence testing procedure. A difference of 3.2 µM (SD 1.5 µM) was observed in adult pediatric-onset treated patients versus controls in Study ENB-009-10 for the change from baseline to Week 6 in PPi. Between 6 and 9 patients per cohort (18 and 27 patients total) will give sufficient power to detect a mean difference of 2.3 to 3.2 µM (SD 1.5 µM).

27 patients who meet eligibility criteria for study participation will be randomized to 1 of the following 3 cohorts:

1. 0.5 mg/kg initial single dose; multiple dosing starting after 2 weeks at 0.5 mg/kg 3 times per week

2. 2.0 mg/kg initial single dose; multiple dosing starting after 2 weeks at 2.0 mg/kg 3 times per week

3. 3.0 mg/kg initial single dose; multiple dosing starting after 2 weeks at 3.0 mg/kg 3 times per week

Randomization will be stratified by gender to ensure a similar distribution of gender in each cohort. An IXRS central randomization scheme will be employed.

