#### **Definition of Treatment Baseline:**

• For PPi and PLP assessments, there are 5 pre-treatment baseline samples (-168, -156, -24, -12h, and pre-dose Day 1) to be collected. The average value will be used for Baseline.

• For antibody, and laboratory assessments, Treatment Baseline is the Day 1 pre-dose sample.

• For Safety assessments (including weight), the last assessment prior to first dose will be used for Treatment Baseline.

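### Entering baseline weight as a median split discards part of what the covariate can explain; a linear term in kg would cost the same single degree of freedom

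*SAP*

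**What the plan says.** SAP 7.2.1 (Primary Endpoint) specifies a REML repeated measures model "adjusted for baseline PPi, gender, baseline weight group" and study drug lot. The weight group has two levels, at or above the median and below it. SAP 7.2.1.5 (Sensitivity Analyses) repeats the term in an ANCOVA "with treatment as fixed factor, baseline PPi, gender, baseline weight group" and lot.

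The one variant of the primary model drops weight altogether: "The same model will additionally be employed with the fixed, categorical effect of visit, adjusted for baseline PPi". The supportive rank tests do not use weight either.

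A baseline weight value is defined in SAP 9.3: "For Safety assessments (including weight), the last assessment prior to first dose will be used for Treatment Baseline". SAP 7.3.3.2 standardises weight to kg for listing. Baseline PPi is named in the same model with no grouping.

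Neither document gives a reason for the cut. Neither says whether the median is taken over all patients or within cohort, or whether it is recalculated when SAP 7.2.1 repeats the analyses in the PP Set.

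**The concern.** A two-level group and a linear term each use one degree of freedom. The group treats everyone on one side of the cut as alike and places a step between two patients who may differ by a kilogram. Weight differences within each group are left unadjusted.

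Two things are at stake. The first is residual variance, which matters with only 6 to 9 patients per cohort and a success rule that needs both comparisons to reject. The second is chance imbalance. Randomisation is stratified by gender only, so weight can differ between cohorts by chance, and the split corrects such a difference only in part. The undefined median adds a specification gap: different readings of the text give different covariates.

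**Working it through.** **The plan's own power figures.** Inputs from SAP 9.2: SD 1.5 µM, two-sided two-sample t-test, no covariates. Alpha is from SAP 7.2.1.4: "A two-sided Type I error rate of 0.05 will be used to define statistical significance". By the noncentral t distribution, per comparison:

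- 9 per cohort, 2.3 µM: 86.3%, against a stated figure above 80%.
- 6 per cohort, 3.2 µM: 91.4%, against a stated figure above 90%.

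Both are reproduced, and neither uses weight.

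**Information kept by the split.** For standard normal X and the indicator of X ≥ median, the covariance is 1/√(2π) and the indicator's variance is 1/4. The squared correlation is (1/(2π)) ÷ (1/4) = 2/π = 0.637, so the loss is 36.3%. Simulation gives:

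- Normal weight: mean loss 36.3% at N = 27 (5th to 95th percentile 26% to 47%) and 36.1% at N = 18 (24% to 49%).
- Other shapes at N = 27: uniform 27%; lognormal with log-SD 0.2, 0.3 and 0.5: 38%, 40% and 45%.
- With gender in the model and an assumed male–female weight difference of 0.5 to 1 SD: 38% to 42%.

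**Residual variance.** Let r be the correlation of weight with PPi change after the other terms. The documents do not give it. Residual variance is proportional to 1 − r² with linear weight and to 1 − 0.637r² with the split. The last column is 27 × (1 − 1/ratio).

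| r | linear | split | ratio | equivalent patients of 27 |
|---|---|---|---|---|
| 0 | 1.000 | 1.000 | 1.000 | 0 |
| 0.1 | 0.990 | 0.994 | 1.004 | 0.1 |
| 0.2 | 0.960 | 0.975 | 1.015 | 0.4 |
| 0.3 | 0.910 | 0.943 | 1.036 | 0.9 |
| 0.4 | 0.840 | 0.898 | 1.069 | 1.7 |
| 0.5 | 0.750 | 0.841 | 1.121 | 2.9 |

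**Power per comparison.** Residual SD is 1.5√(1 − R²) with linear weight and 1.5√(1 − 0.637R²) with the split, where R² = r². Residual degrees of freedom are 27 − 7 = 20 or 18 − 7 = 11: three cohort means plus one each for baseline PPi, gender, weight and lot. The calculation assumes two lots and one model pooled over cohorts, at the single Week 9 timepoint.

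| R² | 9 per cohort, 2.3 µM: linear / split | 6 per cohort, 3.2 µM: linear / split |
|---|---|---|
| 0 | 87.1% / 87.1% | 91.9% / 91.9% |
| 0.05 | 88.7% / 88.2% | 93.1% / 92.7% |
| 0.10 | 90.3% / 89.2% | 94.3% / 93.4% |
| 0.20 | 93.3% / 91.2% | 96.3% / 94.9% |
| 0.30 | 95.9% / 93.0% | 98.0% / 96.2% |

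**Chance imbalance.** In simulated trials of 3 × 9 patients with the split at the overall median, about 38% of a chance weight difference between the 3.0 and 0.5 mg/kg cohorts remained after adjustment for normal weight. For lognormal weight with log-SD 0.3 it was 42% to 43%. A linear term removes all of the linear imbalance.

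**Scope of the median.** SAP 7.2.1 describes the model as fitted for each cohort, so a within-cohort median is a possible reading. With 9 untied weights per cohort, each cohort would then have 5 patients at or above its median and 4 below. The groups would be balanced by construction and would correct none of the imbalance; simulation confirms that 100% remains. If the median is recalculated in the PP Set, a patient can change group with no change in weight.

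**The case against.** The case against is substantial on size.

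- **Weight may matter little.** Protocol 8.4 states: "Weight based (ie, mg/kg) dosing for asfotase alfa allows normalization of dosing across patient populations with different body weights". The first administrative letter adds weekly dose adjustment for weight. The relevant correlation is also what remains after cohort, baseline PPi, gender and lot. This stands: r may be near zero, and the gain would then be near zero. It does not favour the split over a linear term, because weight was chosen for the model.
- **A linear term has its own assumption.** With 18 to 27 patients, one extreme weight can have leverage. This stands as a reason to keep a check, but the split instead assumes a single step at a point set by who enrols.
- **Other analyses do not use weight.** The model adjusted for baseline PPi alone and the exact rank tests do not depend on the cut. This is true, but they cannot show whether the form of the weight term affects the primary result.

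A reader might infer that the trial loses a third of its power or information. The documents do not support that: the 36% concerns a nuisance covariate, not the cohort difference. A reader might also take about 3 of 27 patients as the expected cost, but that needs r = 0.5, and no correlation is given. Nor does the split bias the randomised comparison or inflate Type I error: it is prespecified and does not depend on outcome. The stated power is unaffected, since it comes from an unadjusted t-test.

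**Conclusion.** The point holds as a cheap improvement of low to moderate weight. Both models use a coarser form of weight than the data allow, for the same degree of freedom, and the cut is not fully defined.

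The loss of linear information in the covariate is about 36% for normal weight and a linear effect, and about 27% to 45% for the other distributions tried. The effect on the primary test depends on a correlation that the documents do not give. Excess residual variance runs from 0% at r = 0 to 12% at r = 0.5. A realistic gain is about 0 to 2 points of power per comparison at 9 per cohort.

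**What to change.** In SAP 7.2.1 and 7.2.1.5, replace the two-level weight group with baseline weight in kg as a continuous covariate, prespecified before database lock. Keep the median-split model as a sensitivity analysis, with the median defined once over all FA Set patients and carried unchanged into the PP Set. That covers the linearity and leverage risk.

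The cost is one phrase in each of two sections and one sentence for the retained model. It needs no new data and no extra degree of freedom.
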